5.2 Exclusion Criteria

Subject will be excluded from participation in the study if any of the following apply:

1. Subject is anticipated to require ureteral stenting during surgery.
2. Subject has a history of known retroperitoneal fibrosis.
3. Subject has an active urinary tract infection.
4. Subject has received any investigational therapy within 28 days or 5 half-lives, whichever is longer, prior to screening.
5. Subject has any condition that, in the investigator's opinion, makes the subject unsuitable for study participation.
6. Subject has a known or suspected hypersensitivity to ASP5354, ICG or any components of the formulation used.
7. Subject has had previous exposure to ASP5354.
8. Subject has moderate to severe cardiac disease that limits daily functioning (New York Heart Association Class III-IV) or other medical conditions that the investigator feels would impact safety or study compliance.
9. Subject has a mean resting heart rate ≤ 45 bpm or ≥ 115 bpm, mean systolic blood pressure (SBP) ≥ 160 mmHg or mean diastolic blood pressure (DBP) ≥ 100 mmHg on day -1. If the mean blood pressure exceeds the limits above, repeat readings can be taken. Subject who has adequately controlled blood pressure is eligible.
10. Subject has a mean corrected QT interval (Triplicate ECG) using Fridericia's formula (QTcF) > 430 msec (for male subjects) and > 450 msec (for female subjects) on day -1. If the mean QTcF exceeds the limits above, the mean of 1 additional triplicate ECG may be taken.
11. Subject has any of the following screening laboratory values:
 - Hemoglobin ≤ 9 g/dL

- Absolute neutrophil count $\leq 1500/\mu\text{L}$
 - Platelet count $\leq 100000/\mu\text{L}$
 - eGFR $< 60 \text{ mL}/\text{min}/1.73 \text{ m}^2$ (Not applicable to subjects enrolled after optimal dose determination.)
 - Serum bilirubin $\geq 2 \times$ upper limit of normal (ULN)
 - Aspartate aminotransferase (AST) or serum glutamic oxaloacetic transaminase $\geq 2.5 \times$ ULN
 - Alanine aminotransferase (ALT) or serum glutamic pyruvic transaminase $\geq 2.5 \times$ ULN
12. Subject has taken ICG or other NIR-F imaging agents within 48 hours prior to study treatment administration.
 13. Subject has taken diuretics or inhibitors of renal transporters defined by FDA (see [Appendix 12.6 List of Excluded Concomitant Medications]) within 48 hours prior to study treatment administration.
 14. Subject has used any illicit drugs, unless legally prescribed and is not being abused (amphetamines, barbiturates, benzodiazepines, cannabinoids, cocaine and opiates) within 1 month prior to day -1.
 15. Subject has a history of alcohol abuse. Subject should not have consumed any alcohol within 48 hours of surgery.

Waivers to the exclusion criteria will **NOT** be allowed.

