1. Institutional Review Board (IRB)/Independent Ethics Committee (IEC) approved written informed consent and privacy language as per national regulations (e.g., Health Insurance Portability and Accountability Act authorization for US study sites) must be obtained from the subject prior to any study-related procedures (including withdrawal of prohibited medication, if applicable).
2. Subject is scheduled to undergo laparoscopic/minimally invasive colorectal surgery.
3. Subject will need visualization of the ureter(s).
4. Subject is considered an adult (≥ 18 years of age) according to local regulation at the time of signing the informed consent form.
5. Female subject is not pregnant (see [Appendix 12.3 Contraception Requirements]) and at least 1 of the following conditions apply:
 - a. Not a woman of childbearing potential (WOCBP; see [Appendix 12.3 Contraception Requirements])
 - b. WOCBP who agrees to follow the contraceptive guidance (see [Appendix 12.3 Contraception Requirements]) from the time of informed consent through at least 30 days after final study treatment administration.
6. Female subject must agree not to breastfeed starting at screening and throughout the study period.
7. Female subject must not donate ova starting at first dose of IP and throughout the study period and for 30 days after final study treatment administration.
8. Male subject with female partner(s) of childbearing potential (including breastfeeding partner) must agree to use contraception (see [Appendix 12.3 Contraception Requirements]) throughout the treatment period and for 30 days after final study treatment administration.
9. Male subject must not donate sperm during the treatment period and for 30 days after final study treatment administration.
10. Male subject with pregnant partner(s) must agree to remain abstinent or use a condom for the duration of the pregnancy throughout the study period and for 30 days after final study treatment administration.
11. Subject agrees not to participate in another interventional study while participating in the present study.

Subjects enrolled after optimal dose determination:

12. Subject has any of the following values:
 - Body mass index > 25
 - Estimated glomerular filtration rate (eGFR) ≥ 15 mL/min/1.73 m² and < 60 . Subjects with an eGFR ≥ 60 mL/min/1.73 m² may be considered after discussion with the medical monitor.

Waivers to the inclusion criteria will **NOT** be allowed.

Exclusion Criteria:

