2.1.1.2 Summary of Clinical Data

2.1.1.2.1 Phase 1 Results (Study 5354-CL-0001)

As of the writing of this protocol, 1 clinical study of ASP5354 has completed dosing and study report preparation is ongoing. Study 5354-CL-0001 is a phase 1, double-blind, randomized, placebo controlled, single ascending dose study assessing the safety and pharmacokinetics of ASP5354 in healthy adult volunteers. IP was administered as a single iv bolus injection under fasting conditions.

2.1.1.2.1.1 Pharmacokinetics and Product Metabolism in Humans

Following a single iv administration, ASP5354 was rapidly eliminated. The observed pharmacokinetic parameters suggested a dose proportional increase in the investigated dose range from **CCI** to **CCI**. Almost all fraction of ASP5354 administered was excreted unchanged in urine. Renal clearance was nearly equivalent to the total body clearance.

For details please refer to the current version of the ASP5354 IB.

2.1.1.2.1.2 Safety

Single doses of up to **CCI** were considered safe and tolerable, with no patterns noted for safety concerns in healthy subjects. Twenty subjects received ASP5354 at doses of **CCI**, **CCI**, **CCI** and **CCI** (each in 4 subjects). Ten subjects received placebo for ASP5354 (2 subjects per cohort).

Of the 30 subjects treated with ASP5354 or placebo, 5 subjects experienced at least 1 treatment-emergent adverse event (TEAE; oral herpes, pyelonephritis, urinary tract infection, headache, presyncope, dysuria, nausea, vomiting and incontinence [each in 1 subject]). Two (20.0%) subjects who received placebo experienced TEAEs of nausea, vomiting and incontinence (each in 1 subject); 1 (25.0%) subject who received **CCI** ASP5354 experienced TEAEs of oral herpes and presyncope; 1 (25.0%) subject who received **CCI** ASP5354 experienced a TEAE of urinary tract infection; and 1 (25.0%) subject who received **CCI** ASP5354 experienced TEAEs of dysuria, headache and pyelonephritis. None of the subjects experienced TEAEs considered to be at least possibly related to ASP5354. One subject who received ASP5354, **CCI** experienced a \geq grade 3 TEAE; the grade 3 event of pyelonephritis was also an SAE that was considered by the investigator to be not related to ASP5354; rather, it was assessed as related to the use of a urinary catheter. TEAEs leading to withdrawal of IP were not applicable, as it was a single dose study. No deaths were reported in the study.

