5.1 Inclusion Criteria

Subject is eligible for participation in the study if all of the following apply:

1. Institutional Review Board (IRB)/Independent Ethics Committee (IEC) approved written informed consent and privacy language as per national regulations (e.g., Health Insurance Portability and Accountability Act authorization for US study sites) must be obtained from the subject prior to any study-related procedures (including withdrawal of prohibited medication, if applicable).
2. Subject is scheduled to undergo laparoscopic/minimally invasive colorectal surgery.
3. Subject will need visualization of the ureter(s).
4. Subject is considered an adult (≥ 18 years of age) according to local regulation at the time of signing the informed consent form (ICF).
5. Female subject is not pregnant (see [Appendix 12.3 Contraception Requirements]) and at least 1 of the following conditions apply:
 - a. Not a woman of childbearing potential (WOCBP; see [Appendix 12.3 Contraception Requirements])
 - b. WOCBP who agrees to follow the contraceptive guidance (see [Appendix 12.3 Contraception Requirements]) from the time of informed consent through at least 30 days after final study treatment administration.
6. Female subject must agree not to breastfeed starting at screening and throughout the study period.
7. Female subject must not donate ova starting at first dose of IP and throughout the study period and for 30 days after final study treatment administration.
8. Male subject with female partner(s) of childbearing potential (including breastfeeding partner) must agree to use contraception (see [Appendix 12.3 Contraception

Requirements]) throughout the treatment period and for 30 days after final study treatment administration.

9. Male subject must not donate sperm during the treatment period and for 30 days after final study treatment administration.
10. Male subject with pregnant partner(s) must agree to remain abstinent or use a condom for the duration of the pregnancy throughout the study period and for 30 days after final study treatment administration.
11. Subject agrees not to participate in another interventional study while participating in the present study.

Subjects enrolled after optimal dose determination:

12. Subject has any of the following values at screening:
 - Body mass index > 25

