 - Estimated glomerular filtration rate (eGFR) ≥ 15 mL/min/1.73 m² and < 60. Subjects with an eGFR ≥ 60 mL/min/1.73 m² may be considered after discussion with the medical monitor.

Waivers to the inclusion criteria will **NOT** be allowed.

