The study design is updated to allow the enrollment of additional subjects into the CCI arm after it is determined to be an optimal dose. This revision effects the following sections: 
• Study Schema (Figures 1 and 2)• Study Design Text is added to clarify that the optimal dose cohort may continue enrollment with up to a maximum of 15 subjects. Text is added to Section 9, Statistical Methodology, to clarify that there will be a separate group for the analysis of subjects enrolled after determination of optimal dose.
RATIONALE:
To obtain additional data of ASP5354 in the broadest subject population at the selected optimal dose.
2. Add inclusion criterion for BMI and/or renal impairment
DESCRIPTION OF CHANGE:
An inclusion criterion is added to enroll subjects with a BMI > 25 and/or renal impairment after the optimal dose has been determined.
RATIONALE:
The BMI criterion is added to collect further information on visualization in subjects with high BMI. The estimated glomerular filtration rate (eGFR) criterion is added to collect further information on visualization and pharmacokinetic data in subjects with eGFR < 60.

Nonsubstantial Changes
1. Revise planned study period
DESCRIPTION OF CHANGE:
The completion of the planned study period is changed from 3Q2021 to 4Q2021 .
RATIONALE:
This revision is made to reflect the estimated study completion.
2. Clarify that VRC will be held until the optimal dose is determined

DESCRIPTION OF CHANGE:
Text is added to clarify that the VRC will be held to review subject data until the optimal dose is determined.
RATIONALE:
This revision is made for clarification.
3. Minor Administrative-type Changes
DESCRIPTION OF CHANGE:
Include minor administrative-type changes (e.g., typos, format, numbering and consistency throughout the protocol) and add eGFR to List of Abbreviations.
RATIONALE:
To provide clarifications, administrative changes and corrections to the protocol.

II. Amendment Summary of Changes:

IIA. Substantial Changes

1 Protocol Summary 1.2 Study Schema (Figure 1 Study Schema)
WAS:

Up to 15 subjects will be randomly assigned to receive single doses of ASP5354 at each dose level (CC1, [REDACTED] or CC2).
IS AMENDED TO:

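### After the optimal dose is chosen, no eGFR-specific rule excludes a subject with BMI above 25 and eGFR below 15, because the floor of 15 sits in only one of two alternatives

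*Protocol*

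**What the plan says.** Three pieces of Protocol text govern renal eligibility once the optimal dose is known.

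- **Inclusion 12** (Protocol 5.1) applies only to subjects enrolled after that point. It opens with "Subject has any of the following values at screening" and lists two bullets. The first is BMI above 25. The second is "Estimated glomerular filtration rate (eGFR) ≥ 15 mL/min/1.73 m² and < 60", followed by a sentence allowing subjects with eGFR of 60 or more to be considered after talking to the medical monitor. The synopsis version opens "Subject has any of the following values" and has the same structure.
- **Exclusion 11** (Protocol 5.2) has an eGFR bullet that bars values below 60. It is qualified by "Not applicable to subjects enrolled after optimal dose determination". The synopsis carries the same qualifier.
- **Attachment 1** (Substantial Amendment 2) describes the new criterion as enrolling "subjects with a BMI > 25 and/or renal impairment after the optimal dose has been determined".

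Two other exclusions rest on judgement. Exclusion 5 reads "Subject has any condition that, in the investigator's opinion, makes the subject unsuitable for study participation". Exclusion 8 covers serious cardiac disease or "other medical conditions that the investigator feels would impact safety or study compliance". Sections 5.1 and 5.2 contain no other eGFR limit and no dialysis exclusion.

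**The concern.** The sponsor wrote one numeric renal floor for the expansion, and the layout lets a subject bypass it by qualifying on BMI. Such an enrolment would need no waiver, and on eGFR grounds it would not count as an entry-criteria deviation under Protocol 10.3.

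Renal function matters for this agent. Protocol 2.1.1.2.1.1 reports that nearly all of the dose leaves unchanged in urine and that "Renal clearance was nearly equivalent to the total body clearance". Imaging also depends on the agent flowing from kidney to bladder (Protocol 2.2). The human dosing described is in healthy phase 1 volunteers, and subjects enrolled before optimal-dose determination had to have eGFR of at least 60. The documents describe no human dosing below 60. The amendment deliberately opens the range from 15 to below 60; the gap extends entry below 15 without saying so.

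**Working it through.** The plan gives no figure to reproduce, so the main check is one of logic. All eGFR values are in mL/min/1.73 m².

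**Step 1: the rule after optimal-dose determination.**
- Inclusion 12 is met if BMI > 25 OR 15 ≤ eGFR < 60.
- The eGFR bullet of exclusion 11 does not apply.
- All other criteria are assumed met. None of them is stated in terms of eGFR.
- The medical-monitor option for eGFR ≥ 60 is not coded, because it has no bearing on values below 15.

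**Step 2: enumerate cases.**

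| BMI | eGFR | Before determination | After, as written | After, with a floor of 15 in exclusion 11 |
|---|---|---|---|---|
| 22 or 25 | 5 or 14 | ineligible | ineligible | ineligible |
| 22 or 25 | 15, 45 or 59 | ineligible | eligible | eligible |
| 22 or 25 | 60 or 90 | eligible | ineligible | ineligible |
| 25.1 or 32 | 5 or 14 | ineligible | **eligible** | **ineligible** |
| 25.1 or 32 | 15, 45 or 59 | ineligible | eligible | eligible |
| 25.1 or 32 | 60 or 90 | eligible | eligible | eligible |

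As written, the floor of 15 acts only at BMI ≤ 25. Adding it to exclusion 11 changes the four cells with BMI > 25 and eGFR < 15, and no others.

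**Step 3: test the alternative reading.** If both bullets had to be met (BMI > 25 AND 15 ≤ eGFR < 60), the gap would close. That reading would also bar a subject with BMI 22 and eGFR 45, which conflicts with the opening words of inclusion 12 and with the amendment's own description.

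**Step 4: illustrative exposure.** This rests on assumptions that the documents do not supply: a fixed dose, renal clearance proportional to eGFR, a reference eGFR of 90, and a renal share of clearance *f* of 0.90 to 1.00 at that reference. Exposure relative to the permitted floor is then

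AUC(e)/AUC(15) = [(1 − f) + f × 15/90] / [(1 − f) + f × e/90].

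- f = 0.90: the numerator is 0.10 + 0.15 = 0.25. For e = 10, 8 and 5 the denominators are 0.20, 0.18 and 0.15, giving 1.25, 1.39 and 1.67.
- f = 1.00: the ratio is 15/e, giving 1.50, 1.88 and 3.00.

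By the same formula, exposure at eGFR 15 is 1/0.25 = 4.0 to 90/15 = 6.0 times that at eGFR 90. The plan already accepts that increase, and it is not caused by the gap. At eGFR 8 the extra factor of 1.4 to 1.9 is less than one step of the 3-fold dose spacing in Protocol 4.2.

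**The case against.** The strongest objection concerns intent. The medical-monitor sentence adds little under a pure 'or' reading: a subject with BMI above 25 and eGFR of 60 or more already qualifies. It makes more sense if 15 to below 60 was meant as the default renal range for every expansion subject, with 15 as a general floor. This stands as a doubt about intent. It does not close the gap, because the sentence speaks only to eGFR of 60 or more and the criterion's opening words point to 'or'.

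A second objection is that 15 may only define the renal-impairment alternative. The documents do not say why it was chosen, and the amendment's rationale speaks of the broadest population and of eGFR below 60 without naming a floor. This also stands. Extending 15 to everyone is sensible, but it is partly the reviewer's inference.

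Third, a reader might infer that a subject with BMI 30 and eGFR 8 passes every numeric rule, so that investigator discretion is the only barrier. The documents do not support that. The hemoglobin, neutrophil, platelet, bilirubin, transaminase, heart-rate, blood-pressure and QTcF limits still apply, as do the 48-hour restrictions on diuretics and renal-transporter inhibitors. Only the narrower statement holds: no eGFR-specific rule excludes the subject, and investigator judgement is the remaining barrier if everything else is met.

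Fourth, the consequence is small. The optimal-dose cohort is capped at 15. With the usual first review after 3 subjects per dose, at most 15 − 3 = 12 places remain. Expansion subjects enter after the dose is chosen and form a separate analysis group (Protocol 9, SAP 6.1).

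**Conclusion.** The point holds as a minor error in the eligibility text. After optimal-dose determination, the written rules contain no eGFR limit for a subject with BMI above 25. Confidence is high for that literal logic and does not extend to what the sponsor meant.

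The number of subjects affected is unknown and probably small. Dose selection and the estimates for subjects randomized before it are untouched.

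A reader might infer a safety hazard from the nearly complete renal elimination, but the documents do not show one. Dosing is a single bolus, Protocol 4.2 cites a large safety margin, and the redacted doses prevent any comparison with phase 1 exposure. The exposure ratios are illustration under stated assumptions and are not evidence of harm.

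**What to change.** In exclusion 11, in both Protocol 5.2 and the synopsis, replace the switch-off with a two-part limit: *eGFR below 60 mL/min/1.73 m² if enrolled before the optimal dose is determined; eGFR below 15 mL/min/1.73 m² if enrolled after it.*

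Optionally, state in inclusion 12 whether the medical-monitor discussion for eGFR of 60 or more applies to subjects who already qualify by BMI above 25. The floor alone does not settle that.

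The cost is one line of wording in two places, plus a clarifying sentence if the option is taken. Screening eGFR is already needed for eligibility, so no patients, procedures or analyses are added. The floor removes only subjects with eGFR below 15. It leaves the BMI route open from eGFR 15 upward and the renal-impairment route unchanged.

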5.3 Restrictions During the Study

Not applicable.

5.4 Screen Failures

A screen failure is defined as a potential subject who signed the ICF, but did not meet 1 or more criteria required for participation in the study and was not randomized.

For screen failures, the demographic data, date of signing the ICF, inclusion and exclusion criteria, AEs up to the time of screen failure and reason for screen failure will be collected in the electronic case report form (eCRF).

5.4.1 Rescreening

Rescreening is not allowed. However, in case that the results of screening assessments that do not meet the parameters required by the eligibility criteria (e.g., clinical laboratory tests, vital signs, physical examination, ECGs, etc) may be repeated once within the screening period without the need to register the subject as a screen failure.

6 INVESTIGATIONAL PRODUCT(S)

6.1 Investigational Product Administered

The assigned doses of ASP5354 will be administered as a single dose once the surgical area of interest is in view.

Table 4 Investigational Product(s)

Name	ASP5354
Use	Test Product
Dosage Formulation	Solution for injection
Physical Description	Clear deep green solution
Unit Dose Strength	CCI
Packaging and Labeling	ASP5354 solution will be provided in 10-mL amber glass vials and stored according to the instructions on the label
Route of Administration	Intravenous bolus infusion
Administration Instruction	Administered as a single iv bolus administration under fasting conditions, once the surgical area of interest is in view
IP or Non-IP	IP
Sourcing	Provided by sponsor

IP: investigational product

ASP5354 solution for injection should be stored between -25° and -15°C. ASP5354 vials must be allowed to thaw for at least 1.5 hours at controlled room temperature or may be thawed overnight (not more than 12 hours) under refrigerated conditions (approximately 2° to 8°C). ASP5354 vials must be used for preparation of administration within 4 hours after they are removed from the freezer or refrigerator, respectively. After thawing, the vials should be gently rotated several times to ensure a uniform concentration and to avoid foaming (the concentration in the vials is not uniform after thawing). The thawed ASP5354 is filtered and further diluted with Dextrose 5% in water. The diluted ASP5354 shall be stored at controlled room temperature (20° to 25°C) prior to administration and must be administered within (not more than) 4 hours after penetration of vials.

Refer to the pharmacy manual for detailed information regarding preparation, handling and storage of the IP.

6.2 Preparation/Handling/Storage/Accountability

6.2.1 Packaging and Labeling

All IP used in this study will be prepared, packaged and labeled under the responsibility of qualified personnel at Astellas Pharma Inc. (API), Astellas US Technologies (AUST) or sponsor's designee in accordance with API, AUST or sponsor's designee standard operating procedures (SOPs), Good Manufacturing Practice (GMP) guidelines, International Council for Harmonisation of Technical Requirements for Pharmaceuticals for Human Use (ICH) Good Clinical Practice (GCP) guidelines and applicable local laws/regulations.

Each vial will bear a label conforming to regulatory guidelines, GMP and local laws and regulations that identifies the contents as an investigational drug.

Refer to the pharmacy manual for detailed information regarding packaging and labeling of the IP.

